Part 1 will be an adaptive modified toxicity probability interval (mTPI) design dose escalation study in adult patients with advanced solid tumors to determine the safety profile and the recommended phase 2 dose (RP2D) and treatment schedule of NL-201 as monotherapy. Part 1 will include intravenous (IV) (Schedule A and B), each with up to approximately 50 patients. In addition, there will be backfill cohorts (up to approximately 12 patients in total), at certain DMC-cleared dose levels and schedules, to collect, pharmacokinetic, pharmacodynamic and response data in certain tumor types or to explore additional pre-medication regimens (eg, steroids). The decision to enroll patients into backfill cohorts and to define the patients to be enrolled will be made by the Sponsor. Part 1 will enroll up to approximately 115 adult patients in total. Part 2 will be a Simon 2-stage dose expansion cohort study in patients in 2 indications (up to n = 30 per cohort) with exploratory paired biopsies to estimate the tolerability and antitumor activity of NL-201 as monotherapy in these indications.

Parts 3 and 4 (NL-201 in Combination with Pembrolizumab)

Part 3 will be an adaptive mTPI design dose escalation study in up to 42 adult patients with advanced solid tumors to determine the safety profile, RP2D and treatment schedule of NL-201 in combination with pembrolizumab. Part 4 will be a dose expansion phase in 3 cohorts (up to n = 30 per cohort) to confirm the combination RP2D and obtain additional estimation of pharmacokinetics (PK), pharmacodynamics (PDn), and antitumor activity.

All Parts

Patients will enter the screening period, up to 28 days prior to Cycle 1 Day 1 of treatment. PK, PDn, and exploratory tumor biopsy samples will be obtained per the study Schedule of Events (see [Section 1.3](#)). Tumor response to treatment will be assessed by radiographic evaluation per Response Evaluation Criteria in Solid Tumors (RECIST) 1.1 and RECIST for use in cancer immunotherapy trials (iRECIST) every 6 weeks for 12 weeks, and every 12 weeks thereafter while on study treatment. Patients may continue on treatment until unacceptable toxicity, disease progression per iRECIST with either confirmation or clinical decline, completion of 35 administrations (approximately 2 years) with pembrolizumab (for Parts 3 and 4), withdrawal

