Cytokines		(X)	X	X	X	(X)	X	X		X				
All D1 collections include a pre-dose sample (within 1 h prior to dose of NL-201 or pembrolizumab, if applicable) and a post-dose sample 1 h after EOI (± 15 min) of NL-201. D2 and D4 collected 24 h and 72 h after EOI (± 4 h).
 
(X): Additional post-dose collection 4 h after EOI (± 30 min)

PDn blood samples		X	X	X	X	X	X	X		X				
Optional Part 1 & 2: Tumor biopsy (for PD analyses)	X									X				
Patients who consent to tumor biopsy with readily accessible tumor tissue will have a biopsy performed at screening up to 28 days prior to the first dose (C1D1). Patients will have a 2nd paired biopsy 5 to 9 days after receiving dose at Cycle 2 Day 1 dose (C2D1).

Part 4: Tumor tissue (for PD-L1)	X													
Archival biopsy should be within 5 years of screen date for PD-L1 analysis.
 
If archival tissue not available, perform fresh tumor biopsy if readily accessible.

Part 4: Tumor biopsy (for PD analyses)	X									X		(X)		
Part 4 patients with readily accessible tumor tissue will have a biopsy performed at screening up to 28 days prior to the first dose (C1D1). Patients will have a 2nd paired biopsy 7 (± 2) days after the Cycle 2 dose.
 
(X): EOT collection is optional.

Treatment Visit Window	SCR ^a	Treatment Period ^b (21-day cycles)									EOT ^c	RFU	LTFU ^e	Notes	
		Cycle 1				Cycle 2				Cycle 3+					
		D1	D2	D4	D8	D1	D2	D4	D8	D1					
		0	0	0	±1	±3	0	0	±1	±3					
Efficacy Assessments															
CT scan	(X)	Weeks 1-12: Every 6 weeks (± 3d) Weeks 13+: Every 12 weeks (± 7d)									X ^d	{X}			All scans are calculated from C1D1. RECIST 1.1 and iRECIST assessments continue until disease progression (even if study treatment is discontinued). MRI required only to confirm brain metastasis, if applicable. (X): Completed within 28 days of C1D1. For CR and PR, a scan must be performed at least 4 weeks after initial documentation of response to confirm the response. {X}: Only for Parts 2 and 4, radiologic follow-up will continue until disease progression, start of new therapy, withdrawal of consent, study closure, or death, whichever occurs first.
Study Treatment															
Pre-treatment		X				X				X				Refer to Section 6.1.3.	
NL-201		X				X				X					
Parts 3 and 4 only: Pembrolizumab		X				X				X				To be administered prior to NL-201 (refer to Table 7 for details). Pembrolizumab may be administered up to 35 cycles.	

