AE = adverse event; CR = complete response; CT = computed tomography; CXDX = cycle X day X; D = day; ECG = electrocardiogram; ECHO = echocardiogram; ECOG = Eastern Cooperative Oncology Group; EOI = end of infusion; EOT = end of treatment; iRECIST = Response Evaluation Criteria in Solid Tumors for use in cancer immunotherapy trials; LTFU = long-term follow-up; M = month; MRI = magnetic resonance imaging; PD = progressive disease; PDn = pharmacodynamic(s); PD-L1 = programmed cell death ligand 1; PFTs = pulmonary function tests; PR = partial response; Q3W = every 3 weeks; RECIST = Response Evaluation Criteria in Solid Tumors; RFU = radiological follow-up; SAE = serious adverse event; SCR = screening; WOCBP = women of child bearing potential

- a The screening period is up to 28 days prior Cycle 1 Day 1.
- b All assessments should be performed pre-dose of NL-201 or pembrolizumab, if applicable unless otherwise indicated.
- c Upon permanent discontinuation of study drug for any reason, an end of treatment visit should be scheduled as soon as possible but within 30 days following cessation of study treatment or before patient initiates new anti-cancer therapy, whichever is earlier.
- d For Parts 1 and 3 (Dose Escalation), if study treatment is discontinued for reasons other than death, withdrawal of consent, lost to follow-up, or study closure, a CT scan should be performed at EOT visit (within + 2 weeks) if a post-baseline CT scan has not been performed within 5 weeks prior to the EOT visit.
- e Long-term follow-up assessments occur every 6 months (± 1 month) until death, withdrawal of consent, lost to follow-up, or study closure, whichever occurs first, for a maximum of 2 years after end of treatment. This visit can occur by telephone.

Table 2 Schedule of Events – Schedule B (D1 & D8 Dosing)

	SCR ^a	Treatment Period ^b (21-day cycles)												EOT ^c	RFU	LTFU ^e	Notes
		Cycle 1						Cycle 2				Cycle 3+					
		D1	D2	D4	D8	D9	D11	D1	D2	D4	D8	D1	D8				
Treatment Visit Window		0	0	0	±1	0	0	±3	0	0	±1	±3	±1				
General and Safety Assessments																	
Informed consent	X																
Eligibility criteria	X																
Demography	X																
Medical history	X																
Physical examination	X	(X)			X			X			X	X		X			Full physical exam at screening and end of treatment; brief physical exam at all other time points (ie, C1D8, C2D8, and CXD1). (X): Not required if completed within 7 days of Day 1.
Height	X																

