Public health related exposures during global pandemics	Completion of study procedures may increase the risk exposure to pathogens. In addition, challenges to the logistics of study procedures may arise from quarantines, site closures, travel limitations, or other considerations related to global pandemics.	
If a site or region is actively affected by a global pandemic the following adjustments to the protocol will acutely apply until restrictions are removed:
 
 Windows for the following visits/procedures will be expanded to the following due to operational constraints: 
 Dosing visit - C2+D1 (± 3 days) (All Schedules and Parts) Dosing visit - CXD8 (+ 5 days) (Schedule B or step dosing) Radiology assessment for all visits (± 7 days) Alternative methods for safety assessments (eg, phone contact, virtual visit, alternative location for assessment, including local labs or imaging centers) could be implemented when necessary and feasible. Baseline PFTs are not required. Vaccinations approved for the prevention of infection are allowed if completed at least 14 days before C1D1 or any time after C2D1. SARS-CoV-2 testing will be required as per local regulations. An enrolled patient may have a study drug (NL-201) dosing delay of up to 14 days, if the patient received an approved SARS-CoV-2 immunization or treatment before receiving their first dose of study drug on C1D1 in any schedule.

C = cycle; CD = cluster of differentiation; D = day; DMC = Data Monitoring Committee; ECG = electrocardiogram; eGFR = estimated glomerular filtration rate; GLP = Good Laboratory Practice; HIV = human immunodeficiency virus; ICU = intensive care unit; IV = intravenous; IL = interleukin; SARS-CoV-2 = severe acute respiratory coronavirus 2; PFT = pulmonary function test; ULN = upper limit of normal; WNL = within normal limits

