8.1.2 Treatment Period

Visits will occur per the Schedule of Events ([Section 1.3](#)). The date of the first dose of protocol-required therapies is defined as Day 1. All subsequent doses and study visits will be scheduled based on the Day 1 date. Administration of protocol-required therapies is to be administered last during each visit that it is required, unless otherwise indicated in the Schedule of Events.

After discontinuation from study treatment, patients in Parts 2 and 4, who do not have confirmed disease progression are required to continue disease response assessments and report new anti-cancer treatment per the Schedule of Events ([Section 1.3](#)) and [Section 8.1.5](#). Frequency of these disease response assessments will continue per the Schedule of Events until first subsequent anti-cancer treatment, death, lost to follow-up, withdrawal of consent, or confirmed disease progression, whichever comes first. Following confirmed disease progression, all patients enter long-term follow-up and will be assessed as per the Schedule of Events ([Section 1.3](#)) and [Section 8.1.5](#).

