9.4 Statistical Analyses

9.4.1 General Considerations

Demographic data and disease-related characteristics will be summarized separately for Part 1, by schedule (eg, IV Schedule A, IV Schedule B), and Part 2, by expansion cohort. Descriptive statistics (count and percent, mean, median, standard deviation, minimum, maximum) will be used. All patient data, efficacy and safety data will be summarized. Data from Parts 3 and 4 (NL-201 in combination with pembrolizumab) will be summarized in a similar manner.

A full Statistical Analysis Plan will be prepared to describe in full the statistical methods and analyses to be applied to the data arising in this study.

9.4.2 Determination of MTD in Part 1 and Part 3

For each schedule (IV Schedule A, IV Schedule B) in Part 1 (NL-201 monotherapy), the determination of MTD will be the highest dose for which the probability of a patient experiencing a DLT with NL-201 during Cycle 1 is $\leq 33\%$. Refer to [Section 9.2](#) for more details.

Similarly, for each schedule separately in Part 3 (NL-201 in combination with pembrolizumab), the determination of MTD will be the highest dose for which the probability of a patient experiencing a DLT with NL-201 during Cycle 1 is $\leq 33\%$. Refer to [Section 9.2](#) for more details.

9.4.3 Assessment of Preliminary Efficacy in Part 2 and Part 4

For NL-201 monotherapy, while tumor response data based on both RECIST 1.1 and iRECIST will be collected from all patients in dose escalation and expansion, formal analysis of tumor response will only be performed for the expansion cohorts in Part 2 based on iRECIST. Results will be presented and summarized using an exact 95% binomial confidence interval.

Other response-related efficacy parameters including time to response, duration of response, and clinical benefit rate will be also summarized by Part 2 expansion cohort.

In expansion cohorts in Part 2, OS and progression free survival (defined as the time from study entry to the time of disease progression or death from any cause) will be displayed graphically using Kaplan-Meier plots. Median PFS and OS will be extracted from the Kaplan-Meier plots along with their associated 95% confidence intervals. PFS and OS rates at 3 monthly intervals will also be extracted. Patients who do not experience progression or death will be censored at their last clinic visit contact for the assessment of disease progression.

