non-target lesions and new lesions). For patients with non-measurable disease only at baseline the evaluation of overall response at each assessment is a composite of the non-target lesion response and presence of new lesions as shown below in **Table 19** (ie, non-target lesions only and new lesions). Patients with symptoms of rapidly progressing disease without radiologic evidence will be classified as progression only when clear evidence of clinical deterioration is available and patient is prematurely withdrawn due to ‘disease progression’. In order for SD to be assigned, patients’ lesions must meet the SD criteria at least once after 6 weeks after study entry.

Table 18 Overall Lesion Response at Each Assessment: Patients With Target Lesions (± Non-Target Lesions)

Target Lesions	Non-Target Lesions	New Lesions	Overall Response
CR	CR	No	CR
CR	Non-CR/Non-PD	No	PR
CR	Not evaluated	No	PR
PR	CR	No	PR
PR	Non-PD	No	PR
PR	Not all evaluated	No	PR
SD	CR	No	SD
SD	Non-PD	No	SD
SD	Not all evaluated	No	SD
Not all evaluated	CR/Non-PD/Not all evaluated	No	NE
PD	Any	Yes or No	PD
Any	PD	Yes or No	PD
Any	Any	Yes	PD

CR = complete response; NE = not evaluable; PD = progressive disease; PR = partial response; SD = stable disease

Table 19 Overall Lesion Response at Each Assessment: Patients With Non-Target Lesions Only

Target Lesions	Non-Target Lesions	New Lesions	Overall Response
-	CR	No	CR
-	Non-CR/Non-PD	No	Non-CR/Non-PD
-	Not all evaluated	No	NE
-	Unequivocal PD	Yes or No	PD
-	Any	Yes	PD

CR = complete response; NE = not evaluable; PD = progressive disease; SD = stable disease

Evaluation of lesions and assessment of overall response following on-study interventions

Following any on-study intervention (eg, local radiation, tumor surgery, paracentesis of ascites, pleural effusions, or chemoembolization) the Investigator should continue assessing target lesions quantitatively, non-target lesions qualitatively, and reporting any new lesions. As a general rule, overall response following local interventions will be limited to disease progression

or “NE” (not evaluable) in case criteria for disease progression are not met. However, the Investigator should take into consideration the reason for the on-study intervention (eg, progression of a lesion or shrinkage of a lesion) when providing the overall assessment.

10.6.3 iRECIST Response Assessment

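### The 6-week minimum for stable disease has no scan-window allowance and starts from an undefined date, so whether an on-schedule first scan can support SD depends on the day booked and on how study entry is read

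*Combined protocol and SAP*

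**What the plan says.** **The SD minimum.** Section 10.6.2 (RECIST 1.1) says that, for SD to be assigned, a patient's lesions "must meet the SD criteria at least once after 6 weeks after study entry". No tolerance is given.

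**The scan schedule.** In Section 1.3, Tables 1 to 4 all carry the row "Weeks 1-12: Every 6 weeks (± 3d" and the note "All scans are calculated from C1D1". The synopsis gives the same rhythm: "every 6 weeks for 12 weeks, and every 12 weeks thereafter while on study treatment". Table 5 (Section 2.3.1) widens the window where a site is affected by a pandemic: "Radiology assessment for all visits (± 7 days".

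**The two clocks.** Section 8.1.2 fixes the treatment clock: "The date of the first dose of protocol-required therapies is defined as Day 1". The SD clock starts at study entry, a term the protocol does not define. Section 9.4.3 uses it for PFS, "defined as the time from study entry to the time of disease progression or death from any cause". Section 9.4.6 uses it as the reference for laboratory change, which suggests baseline, and Section 10.1.3 uses it in connection with giving consent. Consent can be well before dosing: "The screening period is up to 28 days prior Cycle 1 Day 1".

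**The concern.** The scan window opens before the SD minimum is reached, at least if both clocks start at C1D1. A site can scan exactly as instructed and produce an assessment that cannot count towards SD. Two patients with the same disease course, SD at the first scan and progression at week 12, could then be given different best responses because one was booked on a Monday and the other on a Thursday.

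The words *at least once* protect anyone who still has SD at week 12. They do not protect a patient who has progressed by then, or who has no later scan. The second case is foreseeable. In Parts 1 and 3 the end-of-treatment scan is not required if one was done in the preceding 5 weeks (Section 8.1.3). In Parts 2 and 4 imaging stops once new anti-cancer therapy begins (Section 8.1.4).

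Best objective response is a secondary endpoint in every part. Clinical benefit rate is exploratory. Leaving the rule to be interpreted later means settling it in an open-label study after outcomes are known.

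**Working it through.** The plan gives no figure to reproduce; the check is day-count arithmetic.

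**Inputs.**
- SD minimum: 6 weeks = 42 days from study entry (Section 10.6.2).
- First scan: 42 ± 3 = 39 to 45 elapsed days after C1D1, 7 permitted days (Section 1.3).
- Pandemic window: 42 ± 7 = 35 to 49 elapsed days, 15 permitted days (Table 5).
- Second scan: 84 ± 3 = 81 to 87 elapsed days.
- Gap *g* from study entry to C1D1: 0 to 28 days if study entry falls within screening.

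Elapsed days are not study days: because the first dose is Day 1, 39 to 45 elapsed days are study Days 40 to 46.

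**Routine window.** A scan at *t* elapsed days qualifies if *t* + *g* ≥ 42, or > 42 if *after* is read strictly.

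| *g* (days) | Days from study entry | Days failing (< 42) | Days failing (≤ 42, strict) |
|---|---|---|---|
| 0 | 39–45 | 3 of 7 | 4 of 7 |
| 1 | 40–46 | 2 | 3 |
| 2 | 41–47 | 1 | 2 |
| 3 | 42–48 | 0 | 1 |
| 4 | 43–49 | 0 | 0 |

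The conflict therefore disappears only when study entry is at least 3 days (strict: 4 days) before C1D1.

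**Pandemic window, *g* = 0.** 35 to 41 days fail: 7 of 15 (8 of 15 if day 42 also fails). Since 35 + 7 = 42, this window is clear only from *g* = 7 (strict: 8).

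**The opposite error.** If study entry is consent 28 days before C1D1, the minimum is reached 42 − 28 = 14 days after first dose. Section 8.2.1 says that all images, including unscheduled ones, should be considered, so SD could be assigned on a scan just over 2 weeks into treatment.

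**How many patients.** The documents give neither a median PFS nor a distribution of scan days, so this is an illustration under stated assumptions: *g* = 0, exponential PFS with a 3-month median, scans spread evenly over the window, and every patient without progression at week 6 counted as SD.

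- S(6 weeks) = 0.727; S(12 weeks) = 0.528.
- Progression between the two scans: 0.727 − 0.528 = 0.199.
- Times 3/7 = 0.085; times 4/7 = 0.113, so roughly 10% of patients.
- With an assumed 2-month median, the same steps give 3.0 to 4.0 patients per 30, or 10% to 13%.

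The figure leans high because responders are not removed and because scans booked on or after the nominal date reduce it. It does not count patients without a later scan. With *g* of 4 days or more, the routine-window figure is zero.

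**The case against.** **Study entry may not mean C1D1.** Section 10.1.3 ties the term to consent, and consent must precede screening procedures that include echocardiography, lung function tests and CT. For many patients that puts *g* above 4 days and removes the loss of SD. This stands, and it is why the low end of the range is near zero. It does not rescue the rule, because usage is mixed, no minimum screening length is stated, and the consent reading makes the minimum too loose.

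**Reach into the expansion cohorts is indirect.** Section 9.4.3 bases formal response analysis in Part 2 on iRECIST and handles Part 4 similarly. The 6-week sentence is in the RECIST 1.1 section; Section 10.6.3 does not repeat it, and Table 21 assigns iSD with no minimum time. The link is footnote a to Table 20, which invokes RECIST 1.1 principles. Under iRECIST a first progression at week 12 is also only unconfirmed. This narrows the effect, but the secondary objective names both criteria.

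**The replacement category is not stated.** Table 18 assigns SD at each assessment without a time condition, and nothing says what best response becomes when the minimum is missed. That it would be progressive disease or not evaluable is an inference. This stands.

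**A separate SAP is promised** (Section 9.4.1) and could set the tolerance. Nothing in the documents provided does so.

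**Stronger readings.** A reader might infer that about three patients in each 30-patient cohort will lose SD. The documents do not support a count: it needs study entry to equal C1D1, an assumed PFS curve and an assumed spread of scan days. The 3 months in Section 4.1.1 is anticipated treatment duration, and treatment may continue past progression. A reader might also infer that the response rate or the Part 2 futility rule is compromised. Both count only CR and PR.

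**Conclusion.** The inconsistency is real and lies in the current text. With study entry at C1D1, 3 to 4 of 7 compliant first-scan days (7 to 8 of 15 under the pandemic window) cannot support SD. With study entry at consent, the rule can admit SD too early. No other section reconciles the two.

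The effect is confined to patients whose only SD assessment is the early scan. It bears on the RECIST 1.1 best response category, on iRECIST only through the RECIST 1.1 principles footnote, and on the clinical benefit rate only if that counts SD, which is an assumption because no formula is given. The SD minimum does not touch ORR, the Simon test, PFS or duration of response, nor the primary safety endpoints. The share of patients affected runs from near zero to roughly 10%, the upper value being an illustration that depends on the assumptions shown. It is a modest point, but one worth settling before expansion data are read.

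**What to change.** Replace the sentence in Section 10.6.2 with: *For SD to be assigned as best response, SD criteria must be met at least once on a scan no earlier than 6 weeks after C1D1 minus the scan window in force (at least 39 days after the C1D1 date; at least 35 days where the pandemic window applies).* All 7 routine days (39 to 45) and all 15 pandemic days (35 to 49) then qualify. State the limits as elapsed days, since 39 days after C1D1 is study Day 40.

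State in Section 10.6.3 whether the same minimum applies to iSD, name the category given when the minimum is not met, and carry the rule into the SAP.

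The cost is a few sentences, with no new data, visits or procedures and no change to patient care.

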6.3 Measures to Minimize Bias: Randomization and Blinding

6.3.1 Randomization

This is an open-label, dose escalation/dose expansion study; patients will not be randomized.

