For Parts 2 and 4 radiologic follow-up should continue until radiologic disease progression, start of a new anti-cancer treatment, loss to follow-up, or death.

CR and PR require confirmation by a repeat assessment no earlier than 4 weeks after the imaging criteria for response is first met.

Tumor images to determine tumor assessment/response rates and PFS will be evaluated based on RECIST 1.1 and additionally on iRECIST. For more detailed guidance on RECIST 1.1 please refer to the original publication³⁰ and 2 further publications should be considered in case of need for further definitions.^{32,33}

For details regarding methods of lesion measurement and tumor response, see [Section 10.6](#).

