9.2 Sample Size Determination

In Part 1, 2 NL-201 monotherapy dosing schedules (IV Schedule A, IV Schedule B) will be evaluated with the goal being to determine the MTD of each schedule. The MTD is defined as the highest dose for which the probability of a patient experiencing a DLT with NL-201 is $\leq 33\%$. Based on the totality of data arising in Part 1, the DMC will determine a RP2D and treatment schedule of NL-201 for Part 2 that will not exceed the MTD.

Dose escalation in Part 1 will be guided by an mTPI design with up to approximately 50 enrolled per schedule as depicted in [Figure 5](#). This design and number of patients per schedule provides a high likelihood of correctly identifying the MTD with approximately one half of the patients (ie, approximately $n = 15$) being exposed to the MTD, very few being exposed to lower, less effective doses and relatively few being exposed to the MTD+1 dose.

In addition, there will be backfill cohorts (up to approximately 12 patients in total), at certain DMC-cleared dose levels and schedules, to collect, pharmacokinetic, pharmacodynamic and response data in certain tumor types or to explore additional pre-medication regimens (eg. steroids). The decision to enroll patients into backfill cohorts and to define the patients to be enrolled will be made by the Sponsor.

Note: “Enrolled” means any patient that has met all of the study inclusion and exclusion criteria and is eligible to receive study drug.

In Part 2, an expansion cohort study will evaluate safety and estimate antitumor activity of NL-201 as a monotherapy at the RP2D in 2 cohorts of patients: (1) melanoma and (2) RCC. A Simon’s 2-stage design will be used for each cohort independently to test the null hypothesis that the true monotherapy response rate is $\leq 2.5\%$ vs the alternative that the true response rate is $\geq 15\%$. In the first stage, 18 patients will be evaluated. If 0/18 objective responses are seen, recruitment to the cohort will be stopped for futility. Otherwise, a further 12 patients will be evaluated for a total of 30 patients. This design provides 80% power and a Type I error rate of 0.031 under the stated null and alternative hypotheses.

In Part 3, with the mTPI study design, the exact number of patients needed to complete the dose escalation is unknown because it depends on the number of cohorts required to reach MTD and the number of patients in each cohort. Dose escalation will be conducted in up to 42 adult

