Overall response will also be assessed using iRECIST. Immunotherapeutics may result in infiltration of immune cells leading to transient increase in the size in malignant lesions, or undetectable lesions becoming detectable. The criteria are identical to those of RECIST 1.1 in many respects but have been adapted to account for instances where an increase in tumor burden, or the appearance of new lesions, does not reflect true tumor progression.

Key differences are described below. All responses defined using iRECIST criteria are designated with a prefix. iRECIST time-point and best overall responses will be recorded separately.

Confirming Progression

Unlike RECIST 1.1, iRECIST requires the confirmation of progression and uses the terms immune unconfirmed progressive disease (iUPD) (unconfirmed progression) and immune confirmed progressive disease (iCPD) (confirmed progression). Confirmatory scans should be performed at least 4 weeks, but no longer than 8 weeks after iUPD.

iCPD is confirmed if further increase in tumor burden, compared to the last assessment, is seen as evidenced by 1 or more of the following:

- Continued increase in tumor burden (from iUPD) where RECIST 1.1 definitions of progression had been met (from nadir) in target, non-target disease or new lesions
 - Progression in target disease worsens with an increase of at least 5 mm in the absolute value of the sum
 - Continued unequivocal progression in non-target disease with an increase in tumor burden
 - Increase in size of previously identified new lesion (s) (an increase of at least 5 mm in the absolute value of the sum of those considered to be target new lesions) or additional new lesions.
- RECIST 1.1 criteria are met in lesions types (target or non-target or new lesions) where progression was not previously identified, including the appearance of additional new lesions.

If iUPD is not confirmed at the next assessment, then the appropriate response will be assigned (iUPD if the criteria are still met, but no worsening, or immune stable disease [iSD], immune partial response [iPR] or immune complete response [iCR] if those criteria are met compared to baseline). As can be seen in [Table 20](#), the prior documentation of iUPD does not preclude assigning iCR, iPR, or iSD in subsequent time-point assessments or as best overall response (BOR) providing that iCPD is not documented at the next assessment after iUPD.

New Lesions

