Non-iUPD/ PD	Non-iUPD/ PD	Yes	iUPD	Remains iUPD unless iCPD confirmed based on increase in size or number of new lesions previously identified

CR = complete response; iCPD = immune confirmed progressive disease; iCR = immune complete response; iPR = immune partial response; iRECIST = RECIST for use in cancer immunotherapy trials; iSD = immune stable disease; iUPD: immune unconfirmed progressive disease; NL = new lesion; NLNT = new lesion-non-target; NLT = new lesion-target; PD = progressive disease; PR = partial response; RECIST = Response Evaluation Criteria in Solid Tumors; SD = stable disease; SOM = sum of measures; TP = time point

- a Using RECIST 1.1 principles. If no pseudoprogression (PSPD) occurs, RECIST 1.1 and iRECIST categories for CR, PR and SD would be the same.
- b In any lesion category.
- c Previously identified in assessment immediately prior to this TP.

All patients will have their immune best overall response (iBOR) from the start of study treatment until the end of treatment classified as outlined in [Table 21](#).

Table 21 iRECIST Best Overall Response (iBOR)

TPR1	TPR2	TPR3	TPR4	TPR5	iBOR
iCR	iCR, iPR, iUPD, NE	iCR, iPR, iUPD, NE	iUPD	iUPD	iCR
iUPD	iPR, iSD, NE	iCR	iCR, iPR, iSD, iUPD, NE	iCR, iPR, iSD, iUPD, iCPD, NE	iCR
iUPD	iPR, iSD, NE	iPR, iSD, iUPD, NE	iPR, iSD, iUPD, NE, iCPD	iPR, iSD, iUPD, NE, iCPD	iPR
iUPD	iSD, NE	PR	iPR, iSD, iUPD, NE	iPR, iSD, iUPD, iCPD, NE	iPR
iUPD	iSD	iSD, iUPD, NE	iSD, iUPD, iCPD, NE	iSD, iUPD, iCPD, NE	iSD
iUPD	iCPD	Anything	Anything	Anything	iCPD
iUPD	iUPD	iCPD	Anything	Anything	iCPD
iUPD	NE	NE	NE	NE	iUPD

CR = complete response; iBOR = immune best overall response; iCPD = immune confirmed disease progression; iCR = immune complete response; iPR = immune partial response; iSD = immune stable disease; iUPD = immune unconfirmed progressive disease; NE = not evaluable that cycle; PD = progressive disease; PR = partial response; TPR = response at that time point

NOTES:

Table assumes a randomized study where confirmation of CR or PR is not required.

Designation "I" for BOR can be used to indicate prior iUPD to aid in data interpretation.

For patients with non-target disease only at baseline, only CR or non-CR/non-PD can be assigned at each TPR but is not shown in the table for ease of presentation.

Source: [Seymour 2017](#)³¹

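### Table 21 classifies best iRECIST response without confirmation of CR or PR, while Section 8.2.1 and the Schedule of Events require it; the responder definition for Part 2 needs aligning

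*Combined protocol and SAP*

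**What the plan says.** **Confirmation required.** Section 8.2.1, which covers assessment by both RECIST 1.1 and iRECIST, states: "CR and PR require confirmation by a repeat assessment no earlier than 4 weeks after the imaging criteria for response is first met". Each of the four Schedule of Events tables (Section 1.3) carries the matching scan instruction: "For CR and PR, a scan must be performed at least 4 weeks after initial documentation of response to confirm the response".

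**Confirmation not required.** Section 10.6.3 has each patient's iBOR, from start to end of treatment, classified by Table 21. The note under that table reads: "Table assumes a randomized study where confirmation of CR or PR is not required". It is the only iBOR classification table in the documents.

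**Design.** Section 6.3.1: "patients will not be randomized".

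**Use of the classification.** Section 9.4.3: "formal analysis of tumor response will only be performed for the expansion cohorts in Part 2 based on iRECIST". Section 9.2 sets the stage-1 rule for each Part 2 cohort: "If 0/18 objective responses are seen, recruitment to the cohort will be stopped for futility". Otherwise 12 more patients are added, for a total of 30. Section 9.2 does not say whether a counted response must be confirmed. Section 9.4.3 adds that Part 4 is analyzed similarly, and Section 9.4.1 announces a separate SAP.

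**The concern.** Two current sections give different answers to the question of who is a responder. A programmer deriving iBOR from Appendix 6 would credit some responses seen once and never confirmed. One working from Section 8.2.1 would not.

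Part 2 contains the study's only formal hypothesis test (Section 9.1) and its only response-based stopping rule, although ORR is a secondary endpoint. The stage-1 boundary is zero responses against one, so a single patient can decide whether a cohort continues. If the definition is left open until the stage-1 count is known, it would be chosen in an open-label trial with the result in view. The Part 4 ORR estimates would probably carry the same ambiguity.

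**Working it through.** **1. Does Table 21 itself credit single-scan responses, or is the note a leftover?** Here iUPD is unconfirmed and iCPD confirmed progression. Two sequences that the rows allow:

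| Row | Scan 1 | Scan 2 | Scan 3 | Scan 4 | Scan 5 | iBOR by Table 21 | Confirmed per 8.2.1? |
|---|---|---|---|---|---|---|---|
| 1 | iCR | iUPD | iUPD | iUPD | iUPD | iCR | No |
| 2 | iUPD | iSD | iCR | iUPD | iCPD | iCR | No |

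Each has one response scan, followed at the next scan by unconfirmed progression. The rows therefore follow the note.

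**2. Stage-1 decision.** Inputs from Section 9.2: 18 patients, stop at 0. Take a cohort with no confirmed response and one patient on a path such as those above.
- Confirmed count: 0/18, so the cohort stops.
- Table 21 count: 1/18, so 12 more patients are enrolled.

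The boundary is not remote. At the null rate of 2.5% the chance of no response is 0.975^18 = 0.634; at 15% it is 0.85^18 = 0.054.

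**3. ORR estimate.** One patient in 30 is 1/30 = 3.3 percentage points. Clopper-Pearson limits for x of n are the 2.5% quantile of Beta(x, n−x+1) and the 97.5% quantile of Beta(x+1, n−x).
- The plan's own example in Table 14, 6/30: 20.0% (7.7%, 38.6%), which reproduces.
- If one of those six is unconfirmed, 5/30: 16.7% (5.6%, 34.7%).

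**4. Can this be turned into an error rate or a power loss?** That needs the share of responses that confirm and the final success cut-off. The documents give neither. The nearest cut-off, at least 3 of 30 with a stop at 0/18, gives a type I error of 0.037 and power of 0.834, against the stated 0.031 and 80%. It does not reproduce the plan's figures and is no base for a further calculation.

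**The case against.** The strongest reply is that the documents already show the intent. Section 8.2.1 introduces both criteria and then requires confirmation. The Schedule of Events repeats it four times, and the summary of changes for Amendment 5.0 records a clarification of the confirming scan. Section 10.6.3 announces "Key differences are described below" and then covers confirmation of progression and new lesions; it does not list dropping confirmation of response. A footnote to Table 20 says the two criteria give the same CR, PR and SD categories when there is no pseudoprogression. Table 21 names its outside source and states its own assumption. All of this stands, and it makes an unadapted table the likeliest explanation. But no section gives precedence, and Section 10.6.3 applies Table 21 to all patients.

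Table 21 also cannot work as a complete algorithm. Seven of its eight rows begin with iUPD and one with iCR, so a patient whose first scan is iSD or iPR has no row. The sequence iUPD, iSD, iSD, iSD, iSD fits both row 3 (iPR) and row 5 (iSD). So the number of listed patterns says nothing about how many patients would be affected. Nor is the table the only best-response text: Section 10.6.3 also says when an earlier iUPD leaves a later response eligible as best response.

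Finally, Sections 9.1 and 9.2 do not cite Table 21 or iBOR. The link runs through Section 9.4.3 and is an inference. The announced SAP, not available here, could define a responder.

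**Conclusion.** The conflict between Table 21 and Section 8.2.1 is real, stands in current text, and should be fixed. Its size per patient needs no assumption about confirmation: 0/18 against 1/18 at stage 1, and 3.3 points of ORR in 30 patients. That it reaches the Simon count rests on reading Section 9.4.3 as governing the objective responses of Section 9.2.

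A reader might infer that the plan intends to count unconfirmed responses. The documents do not support that, since the body text points the other way. A reader might also infer a definite inflation of the type I error, a loss of power, or a rate of discordant stage-1 decisions. That is not supported either: no confirmation share or final cut-off is given, and a calculation crediting every unconfirmed response would be an upper bound, because Table 21 has no row for many response paths.

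**What to change.** 1. Adapt Table 21 and its note to the confirmation rule of Section 8.2.1. Remove the randomized-study assumption, add rows for patients whose first scan is iSD or iPR, and resolve the overlap of rows 3 and 5.
2. State in Sections 9.2 and 9.4.3 that the stage-1 count, the final count and the ORR in Parts 2 and 4 use iCR or iPR confirmed at 4 weeks or later.
3. Let the iBOR window include a confirming scan done in radiologic follow-up. As written it closes at end of treatment, while Section 8.1.4 continues imaging for Part 2 and Part 4 patients who stop treatment without progression.
4. State whether the 2.5% and 15% rates were set for confirmed or unconfirmed responses. If unconfirmed, restate the operating characteristics.
5. Carry the same definition into the announced SAP, before stage-1 data are seen.

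Cost: mostly wording, since the confirming scans are already required. The ORR may be slightly lower. The stage-1 decision may have to wait at least 4 weeks for a confirming scan when the only response in a cohort is recent.
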